4.2.4.4.2. Handling of Missing PsAMRIS Total Score Assessment

If a subject does not have any results within the visit window (referred to Section 4.2.4.1), the PsAMRIS results for this subject will be considered as missing at the time point, no imputation is needed and the detailed statistical analysis will be described in section 6.1

4.2.4.5. Whole Body-MRI (WB-MRI)

[figure not shown]
Selected peripheral joints and entheses, [REDACTED] will be assessed by WB-MRI.

[figure not shown]

For completed details on the reading, scoring, and review process, please refer details in the Imaging Charter.

The parameters for WB-MRI are listed below:

- SPARCC spine and sacroiliac joint indices
- MRI inflammation indices of peripheral arthritis and enthesitis

[figure not shown]
[figure not shown]
[figure not shown]
[figure not shown]

Figure 4: Areas to be scored for the Peripheral Arthritis and Enthesitis.

The range of total synovitis joints is 0-249, the range of total osteitis joints is 0-288, the range of total osteitis entheses is 0-102, and the range of total STI is 0-99.

4.2.4.8. Handling of Missing [REDACTED]

If a subject does not have any results within the visit window (referred to Section 4.2.4.1), the [REDACTED] results for this subject will be considered as missing at the time point, no imputation is needed and the detailed statistical analysis will be described in section 6.1.

4.2.4.9. Tender and Swollen Joint Counts

For tender and swollen joint counts, a joint assessment will be recorded as “Temporarily Not Assessable Due to IA Injection” (TNA-IA), “Permanently Not Assessable” (PNA), “Temporarily Not Assessable – Other” (TNA-O), “Tender Only”, “Swollen Only”, or “Tender and Swollen”. In this section, the term “assessed” refers to the joints that are “Tender Only”, “Swollen Only”, or “Tender and Swollen”.

The approaches below used to handle joints at screening, baseline and post-baseline visits will be applied, unless otherwise specified.

Table 3: TJC and SJC Handling method

Visit	Scenarios	Handling method
Screening Visit	The joint is assessable	Count it into the number of tender/swollen joints
	The joint is PNA	Exclude it from joint count throughout the study
	The joint is TNA-IA or TNA-O	Exclude it from joint count at screening visit
Baseline Visit	The joint is assessable	Count it into the number of tender/swollen joints
	The joint is TNA-IA or PNA or TNA-O	Exclude it from joint count throughout the study (both baseline and post-baseline visits)
Post-Baseline Visit	The joint is assessable at both baseline and post-baseline visit	Count it into the number of tender/swollen joints
	The joint is TNA-IA or PNA or TNA-O	The last observed joint assessment (including baseline and post-baseline assessment) will be carried forward to this visit

After applying these data handling rules, TJC will be calculated by adding the number of tender joints with outcomes of ‘Tender Only’ or ‘Tender and Swollen’. SJC will be calculated by adding

the number of joints with outcomes of 'Swollen Only' or 'Tender and Swollen'. TJC and SJC will be derived based on all the joints (76 joints for swellingness and 78 joints for tenderness).

Data resource: Joint assessment is entered by evaluator via site pad provided by eRT.

Swollen Joint Count/Tender Joint Count over 48 weeks based on all joints will be presented graphically. Proportion of Subjects with Swollen Joint Count/Tender Joint Count ≤ 1 Over 48 Weeks will be plotted.

4.2.4.10. Subject's Pain Numeric Rating Scale

The pain Numeric Rating Scale (NRS) is the subject's assessment of how much pain he/she had, on average, in the previous week in his/her joints due to Psoriatic Arthritis (PsA). The subject will be asked to mark the box with an X on a 0- to 10-unit NRS on which the left-hand box of 0 represents "No Pain," and the right-hand box of 10 represents "Pain As Bad As You Can Imagine". This value will be used as a numerical result.

Data resource: Subject's pain score is entered by patient via site pad provided by ERT.

Patient's assessment of pain over 48 weeks will be presented graphically.

4.2.4.11. Patient's Global Assessments of Disease Activity (PGA)

The Patient's (Subject's) Global Assessments of Disease Activity is an assessment of how active a subject's PsA was on average during the previous week. Subject will select a number from a 0- to 10-unit NRS on which the 0 represents "Very Well" and 10 represents "Very Poor".

Data resource: PGA is entered by patient via site pad provided by ERT.

4.2.4.12. Evaluator's Global Assessments of Disease Activity (EGA)

The Evaluator's Global Assessment (EGA) is an assessment of how active a subject's arthritis today. Evaluator will select a number from a 0- to 10-unit NRS on which the 0 represents "No Arthritis Activity" and 10 represents "Extreme Active Arthritis".

Data resource: EGA is entered by evaluator via site pad provided by ERT.

4.2.4.13. Clinical Disease Activity Index for Psoriatic Arthritis (c-DAPSA) Score

[figure not shown]
The c-DAPSA is a measure of PsA disease activity, associated with functional and structural outcomes (Aletaha, 2017). The c-DAPSA score is computed using the following formula:

$$\text{c-DAPSA} = \text{TJC68} + \text{SJC66} + \text{PGA} + \text{Pain},$$

where the TJC68 is the 68-tender joint count (0-68), the SJC66 is the 66-swollen joint count (0-66), PGA is the patient (subject) global assessment of disease activity (0-10 NRS), and Pain is the subject's pain numeric rating scale (0-10 NRS).

10 joints (CMC and DIP 2-5 joints on left and right side) will be excluded from TJC78 and SJC76. See Figure 5 for the schematic diagram.

Figure 5: Schematic diagram of 68 tenders and 66 swollen joint assessment

The c-DAPSA score ranges from 0 to 154, and it will be set to missing if any of the 4 components is missing. A higher score indicates greater disease activity. Proposed cut off for c-DAPSA are a score ≤ 4 for remission, a score > 4 and ≤ 13 for low disease activity, > 13 and ≤ 27 for moderate disease activity and > 27 for high disease activity. The proportion of subjects who achieve PSA remission, low disease activity, moderate disease activity and high disease activity will be summarized.

c-DAPSA score over 48 weeks will be tabulated and presented graphically.

4.2.4.14. Enthesitis

Enthesitis or the inflammation of the sites where tendons or ligaments insert into the bone, is a prominent clinical manifestation in subjects with PsA. In this study, Spondyloarthritis Research Consortium of Canada (SPARCC) and Leeds Enthesitis Index (LEI) will be used to evaluate enthesal inflammation. The details about SPARCC and LEI are mentioned in Sections 4.2.4.14.1 and 4.2.4.14.2.

Pre-existing SPARCC enthesopathy is defined as subjects who have a baseline SPARCC score greater than 0. Pre-existing LEI enthesopathy is defined as subjects who have a baseline LEI score greater than 0. The subjects with baseline SPARCC enthesitis is defined as the subjects whose baseline SPARCC scores greater than 0. The subjects with baseline LEI enthesitis is defined as the subjects whose baseline LEI scores greater than 0. Spondyloarthritis Research Consortium of Canada (SPARCC)

The SPARCC Enthesitis Index will be assessed through physical examination of the following sites:

- Medial epicondyle (left/right [L/R])
- Lateral epicondyle (L/R)
- Supraspinatus insertion into greater tuberosity of humerus (L/R)
- Greater trochanter (L/R)
- Quadriceps insertion into superior border of patella (L/R)
- Patellar ligament insertion into inferior pole of patella or tibial tubercle (L/R)
- Achilles tendon insertion into calcaneum (L/R)
- Plantar fascia insertion into calcaneum (L/R)

Tenderness on examination is recorded as either present (1) or absent (0) for each of the 16 sites, for an overall score range of 0–16. Higher count represents greater enthesitis burden.

Similar to the tender and swollen joint assessments, the SPARCC assessment may be not done or the joints may be recorded as “Temporarily Not Assessable” or “Permanently Not Assessable”, thus the approaches of dealing with not done assessment and handling joints that are not assessable will be employed (see Section [4.2.4.9](#) for details).

Data resource: SPARCC questionnaire is entered by evaluator via site pad provided by ERT.

4.2.4.14.1. Leeds Enthesitis Index (LEI)

The Leeds Enthesitis Index will be assessed through physical examination of the following sites. Tenderness (yes/no) will be assessed at 6 sites of tendon insertions (0-6) as depicted below:

- Lateral epicondyle, left and right
- Medial femoral condyle, left and right
- Achilles tendon insertion, left and right

Tenderness on physical examination is recorded as either present (1) or absent (0) for each of the 6 sites, for an overall score range of 0 to 6. Higher count represents a greater enthesitis burden.

Similar to the tender and swollen joint assessments, the LEI assessment may be not done, or the joints may be recorded as “Temporarily Not Assessable” or “Permanently Not Assessable”, thus the approaches of dealing with assessments that are not completed and handling of joints that are not assessable will be employed (see Section [4.2.4.9](#) for details).

Data resource: LEI is entered by evaluator via site pad provided by ERT.

LEI score over 48 weeks will be presented graphically.

4.2.4.15. Dactylitis

Dactylitis (“sausage digit”) is characterized by the swelling of the entire finger or toe. It will be assessed using the Leeds Dactylitis Index (LDI) ([Helliwell, 2005](#)).

4.2.4.15.1. Leeds Dactylitis Index (LDI)

In this study, the dactylitis will be assessed by LDI, which is a function of finger circumference and tenderness (0 = No Tenderness, 1 = Tender, 2 = Tender and wince, 3 = Tender and withdraw).

In addition, as part of the LDI, number of affected digits will be evaluated. Each digit on the hands and feet will be rated as zero for no dactylitis or 1 for dactylitis present. The dactylitis score is the sum of the individual scores for each digit.

The dactylitis score for individual affected finger or toe is defined as below.

$[(\text{Circumference of involved digit}/\text{circumference of contralateral digit} - 1) * 100] * \text{Tenderness Score}$.

Preexisting dactylitis will be defined as subjects who have a baseline LDI score greater than 0 . A higher score indicates greater disease activity.

Data resource: LDI is entered by evaluator via site pad provided by ERT.

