## APPENDIX H. LEEDS DACTYLITIS INDEX (LDI)

The LDI ([Healy, 2008a](#); [Helliwell, 2005](#)) measures the ratio of the circumference of the affected digit to the circumference of the digit on the opposite hand or foot, using a minimum difference of 10% to define a dactylitic digit. The ratio of circumference is multiplied by a tenderness score.

Affected fingers are marked on a diagram displaying fingers and toes. Circumferences of the affected and contralateral fingers are then measured around the proximal phalanx, as close as possible to the web space, using either a measuring tape or a pre-calibrated loop.

The clinician then squeezes the affected fingers with moderate pressure and documents the patient's response: 0 = no tenderness, 1 = tender, 2 = tender and winces, and 3 = tender and withdraws.

Approved

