## APPENDIX H. LEEDS DACTYLITIS INDEX (LDI) (CONTINUED)

The ratio of circumference between an affected finger and the contralateral unaffected finger is recorded. If both sides are affected, the circumference of the affected finger is compared to normative data supplied in a table. The tenderness score (0-3) for a finger with dactylitis is recorded, and a total score is generated for each finger. If multiple fingers are affected, each score is added together to produce a total for the patient.

In addition, as part of the LDI, number of affected digits will be evaluated. Each digit on the hands and feet will be rated as zero for no dactylitis or 1 for dactylitis present. The dactylitis score is the sum of the individual scores for each digit.

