### DACTYLITIS SCORE SHEET

Addressograph Label
---------------------

Date:

Please indicate dactylitic joints

Finger or toe	Circumference involved digit (A)	Circumference contralateral Digit (or Table) (B)	Tenderness score (C)	Final score: $[(A/B) - 1] \times 100 \times C$
TOTAL				

Standard reference: Table - hands

Digit	Men	Women
Thumb	70	58
Index	63	54
Middle	63	54
Ring	59	50
Little	52	44

Table - feet

Digit	Men	Women
Great toe	82	72
Second	52	46
Middle	50	44
Fourth	50	44
Little	52	45

Tenderness score: response to squeeze

0 no tenderness  
1 tender  
2 tender and wince  
3 tender and withdraw

Approved

[figure not shown]
Approved

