4.2.1.2. Secondary Efficacy Endpoints

[figure not shown]
- Change from baseline in the composite score of BME, synovitis, and tenosynovitis assessed by PsAMRIS at Week 48.
- Change from baseline in the composite score of BME and synovitis assessed by PsAMRIS at Weeks 24 and 48.
- Change from baseline in the PsAMRIS total inflammation score (BME, synovitis, tenosynovitis and periarticular inflammation) at Weeks 24 and 48.
- Change from baseline in BME assessed by PsAMRIS at Weeks 24 and 48.
- Change from baseline in synovitis assessed by PsAMRIS at Weeks 24 and 48.
- Change from baseline in tenosynovitis assessed by PsAMRIS at Weeks 24 and 48.
- Change from baseline in periarticular inflammation assessed by PsAMRIS at Weeks 24 and 48.

- Change from baseline in the PsAMRIS total damage score (erosion + bone proliferation) at Weeks 24 and 48.
- Change from baseline in bone erosion assessed by PsAMRIS at Weeks 24 and 48.
- Change from baseline in bone proliferation/enthesophytes assessed by PsAMRIS at Weeks 24 and 48.
- Change from baseline in the Swollen Joint Count (SJC) at Weeks 24 and 48.
- Change from baseline in the Tender Joint Count (TJC) at Weeks 24 and 48.
- Change from baseline in the Clinical Disease Activity Index for Psoriatic Arthritis (c-DAPSA) Score at Weeks 24 and 48.
- Change from baseline in Spondyloarthritis Research Consortium of Canada (SPARCC), in subjects with preexisting enthesopathy at Weeks 24 and 48.
- Change from baseline in the Leeds Enthesitis Index (LEI), in subjects with preexisting enthesopathy at Weeks 24 and 48.
- Proportion of subjects with baseline enthesitis whose enthesitis improves to 0 at Weeks 24 and 48.
- Change from baseline in the Leeds Dactylitis Index (LDI), in subjects with preexisting dactylitis at Weeks 24 and 48.
- Proportion of subjects with baseline dactylitis whose tender dactylitis count improves to 0 at Week 24 and 48.
- Change from baseline in the Psoriatic Arthritis Disease Activity Score (PASDAS) at Weeks 24 and 48.
- Change from baseline in the evaluator's global assessment of disease activity at Weeks 24 and 48.
- Change from baseline in the subject's global assessment of disease activity at Weeks 24 and 48.
- Change from baseline in the subject's assessment of pain at Weeks 24 and 48.
- Change from baseline in Health Assessment Questionnaire-Disability Index (HAQ-DI score) at Weeks 24 and 48.

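### The SAP's Leeds Dactylitis Index formula omits the protocol's reference-table divisor for bilateral dactylitis, so read literally it scores such pairs near zero

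*SAP*

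**What the plan says.** SAP 4.2.4.15.1 defines the score of an affected finger or toe as its circumference relative to the opposite digit, "circumference of contralateral digit} - 1) * 100", multiplied by the tenderness score (0 to 3). It mentions no reference table, no rule for disease on both sides and no size threshold. It then sets the analysis subset: "Preexisting dactylitis will be defined as subjects who have a baseline LDI score greater than 0". SAP 4.2.1.2 lists the endpoint that uses this subset: "Change from baseline in the Leeds Dactylitis Index (LDI), in subjects with preexisting dactylitis at Weeks 24 and 48".

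Protocol Appendix H is fuller. It describes the ratio to the opposite digit, "using a minimum difference of 10% to define a dactylitic digit", and then adds: "If both sides are affected, the circumference of the affected finger is compared to normative data supplied in a table". The divisor column on its score sheet is headed "Circumference contralateral Digit (or Table) (B)", and reference values by sex and digit follow under "Standard reference: Table - hands", with a second table for feet. Digit scores are summed: "If multiple fingers are affected, each score is added together to produce a total for the patient".

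No other SAP section restores the table rule, and SAP 4.2.4.15.1 does not refer to Appendix H.

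**The concern.** The opposite digit is a sensible divisor only if it is not swollen. When the same digit is dactylitic on both sides, the ratio compares two swollen digits. It falls near 1, and the larger digit's small positive score is offset by a negative score for the smaller one.

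Two consequences follow for the LDI-change endpoint. First, a subject with tender bilateral dactylitis can total 0 or less and be classed as having none. Second, a subject who stays in starts from a baseline that is too low. If one digit of the pair heals, the other is now compared with a normal digit and its score rises, so clinical improvement is recorded as worsening. The baseline summaries in SAP 9.2 (LDI in subjects with pre-existing dactylitis, and pre-existing dactylitis yes/no) carry the same error.

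**Working it through.** The plan states no figure to reproduce here, so the check applies both rules to the same digits.

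**Inputs.** The reference circumferences come from the Appendix H score sheet: 54 for a woman's middle finger and 63 for a man's index finger (the sheet prints no unit; mm is assumed). Digit circumferences and tenderness scores are assumed for illustration. Measured against 54, digits of 62 and 60 are 14.8% and 11.1% larger, so both pass the 10% threshold.

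**Formula.** Digit score = (A/B - 1) × 100 × C, summed over affected digits. Under the SAP text, B is the opposite digit. Under Appendix H, B is the table value when both sides are affected.

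**Woman, both middle fingers affected**

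| Circumferences | Tenderness | Appendix H (B = 54) | SAP (B = opposite digit) |
|---|---|---|---|
| 62 / 60 | 2 / 2 | 29.6 + 22.2 = 51.9 | 6.7 - 6.5 = 0.2 |
| 61 / 61 | 2 / 2 | 25.9 + 25.9 = 51.9 | 0 + 0 = 0 |
| 62 / 60 | 1 / 3 | 14.8 + 33.3 = 48.1 | 3.3 - 9.7 = -6.3 |

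Totals are rounded after summing.

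**Why the SAP total collapses.** For a pair a, b with equal tenderness C, the SAP sum is 100 × C × (a/b + b/a - 2) = 100 × C × (a - b)²/(ab). This is zero only if a = b and is otherwise small and positive: for 62/60 and C = 2 it is 200 × 4/3720 = 0.2. With unequal tenderness the sum can be moderately positive or negative. It goes below zero when the smaller digit is sufficiently more tender, as in the third row.

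**Membership of the subset.** The second and third rows give 0 and -6.3 and fail the baseline test of LDI above 0. The first row gives 0.2 and passes.

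**Change when one digit heals.** Start from the first row. The 62 mm finger returns to 54 mm and is no longer tender; the other stays at 60 mm with tenderness 2. The opposite digit is now unaffected, so both rules give (60/54 - 1) × 100 × 2 = 22.2.
- Appendix H: 22.2 - 51.9 = -29.6 (improvement; unrounded 22.22 - 51.85).
- SAP: 22.2 - 0.2 = +22.0 (worsening).

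**A subject kept in by another digit.** Take a man with both index fingers at 75 mm and tenderness 2, plus one ring finger at 70 mm against an unaffected 59 mm, tenderness 2. The ring finger scores (70/59 - 1) × 200 = 37.3 under both rules. The index pair scores 2 × (75/63 - 1) × 200 = 76.2 under Appendix H and 0 under the SAP. Baseline is therefore 113.5 against 37.3. If one index finger heals to 63 mm and is non-tender, the visit total is 37.3 + 38.1 = 75.4 under both, and the change is -38.1 against +38.1.

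**How many subjects.** The documents do not say. For scale only, Protocol Table 4 reports 84 of 176 subjects (47.7%) with pre-existing dactylitis in the 30 mg arm of an earlier apremilast trial. Applied to 120 subjects, that is about 57. If 5% to 30% of those had the same digit affected on both sides, which is an assumption, about 3 to 17 subjects would be exposed.

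**The case against.** The strongest answer is that the table rule may already operate at data entry. On the protocol's score sheet the divisor is a recorded field that can hold the table value, and the SAP says that the evaluator enters the LDI on the site pad. If the pad stores that value, the SAP formula applied to the recorded divisor returns the Appendix H score and no harm occurs. This stands as a condition on the consequence. The pad specification is not in the documents, however, and the SAP names the contralateral digit, not the recorded divisor.

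The wording could also be shorthand. Appendix H itself opens with the unqualified ratio and adds the exception later, and Protocol 6.4.5.8 omits the exception too. But Appendix H does supply it. The SAP presents itself as the more detailed document and spells out conditional scoring rules for HAQ-DI, BASDAI and PsAID-12. A programmer working from it alone would code the opposite digit.

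A reader might infer that both dactylitis endpoints rest on the ratio. They do not. The other endpoint asks whether a tender dactylitis count reaches 0, and a count does not use the ratio. Only its denominator is exposed, and only if baseline dactylitis is read as LDI above 0. The SAP gives that definition for pre-existing dactylitis and does not define baseline dactylitis separately.

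A reader might also infer that every subject with bilateral disease is dropped. That is too strong. Exclusion requires bilateral pairs that sum to 0 or less, with no other digit to offset them. False worsening requires a subject who stays in and one digit of a pair that heals while the other persists.

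**Conclusion.** The SAP derivation is wrong as written: it conflicts with Appendix H, and following it literally gives incorrect LDI scores for same-digit bilateral dactylitis. In the illustrations a protocol score of 48 to 52 becomes a value between -6.3 and 0.2, and an improvement of 29.6 becomes a worsening of 22.0. The digit sizes and tenderness scores are assumed. The near-cancellation at equal tenderness is not: it follows algebraically whenever the two circumferences are close.

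Whether reported results would be wrong depends on what the site pad stores, and how far depends on the unstated share of subjects with bilateral disease. The documents therefore do not support a claim that the trial's dactylitis results will be wrong. The effect is confined to the LDI-change secondary endpoint, the related baseline summaries and, on one reading, the denominator of the tender-count endpoint. The dactylitis counts, PASDAS (which uses a count), the primary endpoint and the sample size are unaffected. The SAP should be corrected before database lock.

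**What to change.** In SAP 4.2.4.15.1, define the divisor as: *circumference of the contralateral digit if that digit is unaffected; otherwise the sex- and digit-specific reference circumference in Protocol Appendix H (column B of the score sheet)*. State that pre-existing dactylitis is derived from this corrected LDI, carry over the 10% threshold, and say whether baseline dactylitis in the tender-count endpoint means the same subset.

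No separate redefinition of pre-existing dactylitis is needed. With the table divisor and the 10% threshold, each dactylitic digit contributes a positive score exactly when it is tender, so LDI above 0 already means at least one tender dactylitic digit.

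The cost is a sentence or two in the SAP and a check of what the site pad records in column B. If it holds only the raw opposite-digit circumference, the program needs a short lookup table. Digit, circumference and tenderness are on the score sheet and sex is in demographics, so no new data are required.
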